### The investigator must ensure that females of childbearing potential:

- Comply with the conditions for pregnancy risk minimization, including confirmation that she has an adequate level of understanding
- Acknowledge the aforementioned requirements

For a female NOT of childbearing potential, pomalidomide is contraindicated unless the following are met (ie, all females NOT of childbearing potential must be counseled concerning the following risks and requirements prior to the start of pomalidomide study therapy):

- She acknowledges that she understands the hazards and necessary precautions associated with the use of pomalidomide

The effect of pomalidomide on spermatogenesis is not known and has not been studied.

Therefore, male subjects taking pomalidomide must meet the following conditions (ie, all males must be counseled concerning the following risks and requirements prior to the start of pomalidomide study therapy):

- Understand the potential teratogenic risk if engaged in sexual activity with a woman of childbearing potential
- Understand the need for the use of a condom, even if he has had a vasectomy, if engaged in sexual activity with a female of childbearing potential.

### **Contraception**

Females of childbearing potential enrolled in this protocol must agree to use 2 reliable forms of contraception simultaneously or to practice complete abstinence from heterosexual intercourse during the following time periods related to this study: 1) for at least 28 days before starting study drug; 2) while participating in the study; 3) dose interruptions; and 4) for at least 28 days after study treatment discontinuation.

The 2 methods of reliable contraception must include 1 highly effective method and 1 additional effective (barrier) method. An FCBP must be referred to a qualified provider of contraceptive methods if needed.

The following are examples of highly effective and additional effective methods of contraception:

- Highly effective methods:
  - Intrauterine device (IUD)
  - Hormonal (birth control pills, injections, implants)
  - Tubal ligation
  - Partner's vasectomy
- Additional effective methods:
  - Male condom
  - Diaphragm
  - Cervical cap

Because of the increased risk of venous thromboembolism in patients with multiple myeloma taking pomalidomide and dexamethasone, combined oral contraceptive pills are not recommended. If a subject is currently using combined oral contraception the subject should switch to another one of the effective methods listed above. The risk of venous thromboembolism continues for 4–6 weeks after discontinuing combined oral contraception.

The efficacy of contraceptive steroids may be reduced during co-treatment with dexamethasone.

Implants and levonorgestrel-releasing intrauterine systems are associated with an increased risk of infection at the time of insertion and irregular vaginal bleeding.

Prophylactic antibiotics should be considered, particularly in subjects with neutropenia.

### **Pregnancy testing**

Medically supervised pregnancy tests with a minimum sensitivity of 50 mIU/mL must be performed for females of childbearing potential, including females of childbearing potential who commit to complete abstinence, as outlined below.

### **Before starting study drug**

#### **Female Subjects**

Females of childbearing potential must have 2 negative pregnancy tests (sensitivity of at least 50 mIU/mL) prior to starting pomalidomide. The first pregnancy test must be performed within 10–14 days prior to the start of pomalidomide and the second pregnancy test must be performed within 24 hours prior to the start of pomalidomide. The subject may not receive study drug until the investigator has verified that the results of these pregnancy tests are negative.

#### **Male Subjects**

Males must practice complete abstinence or agree to use a condom during sexual contact with FCBP while participating in the study, during dose interruptions, and for at least 90 days following study drug discontinuation, even if he has undergone a successful vasectomy.

**During study participation and for 28 days following study drug discontinuation**

**Female Subjects**

- Females of childbearing potential with regular or no menstrual cycles must agree to have pregnancy tests weekly for the first 28 days of study participation and then every 28 days while on study, at study discontinuation, and at Day 28 following study drug discontinuation. If menstrual cycles are irregular, the pregnancy testing must occur weekly for the first 28 days and then every 14 days while on study, at study discontinuation, and at Days 14 and 28 following study drug discontinuation.
- At each visit, the investigator must confirm with the FCBP that she is continuing to use 2 reliable methods of birth control.
- Counseling about pregnancy precautions and the potential risks of fetal exposure must be conducted at a minimum of every 28 days.
- If pregnancy or a positive pregnancy test does occur in a study subject, pomalidomide must be immediately discontinued.
- Pregnancy testing and counseling must be performed if a subject misses her period or if her pregnancy test or her menstrual bleeding is abnormal. Study drug treatment must be discontinued during this evaluation.
- Females must agree to abstain from breastfeeding during study participation and for at least 28 days after study drug discontinuation.

**Male Subjects**

- Counseling about the requirement for condom use during sexual contact with FCBP and the potential risks of fetal exposure must be conducted at a minimum of every 28 days.
- If pregnancy or a positive pregnancy test does occur in the partner of a male study subject during study participation, the investigator must be notified immediately.

**Additional precautions**

- Subjects should be instructed never to give this medicinal product to another person and to return any unused capsules to the investigator at the End-of-Treatment.
- Subjects should not donate blood during therapy and for at least 28 days following discontinuation of pomalidomide.
- Male subjects should not donate semen or sperm during therapy or for at least 90 days following discontinuation of pomalidomide.
- Only enough pomalidomide for 1 cycle of therapy may be dispensed with each cycle of therapy.

**Appendix I. Pomalidomide Education and Counselling Guidance Document**  
**Protocol Number: 20160104**

Patient Name (Print): \_\_\_\_\_ DOB: \_\_\_\_\_ / \_\_\_\_\_ / \_\_\_\_\_ (dd/mm/yyyy)

**Female**

**If female, check one:**

- FCBP (female of childbearing potential): Sexually mature female who: 1) has not undergone a hysterectomy (the surgical removal of the uterus) or bilateral oophorectomy (the surgical removal of both ovaries) or 2) has not been naturally postmenopausal (amenorrhea following cancer therapy does not rule out childbearing potential) for at least 24 consecutive months (ie, has had menses at any time during the preceding 24 consecutive months)
- NOT FCBP

**To be completed prior to each dispensing of pomalidomide**

**Do Not Dispense pomalidomide if:**

- The patient is pregnant.
- No pregnancy tests were conducted for a FCBP.
- The patient states she did not use TWO reliable methods of birth control (unless practicing complete abstinence of heterosexual intercourse) [at least 28 days prior while taking pomalidomide, during dose interruption, and 28 days after discontinuation of pomalidomide].

**FCBP**

1. **I verified that the required pregnancy tests performed are negative.**
2. **I counseled FCBP regarding the following:**
  - Potential fetal harm: If pomalidomide is taken during pregnancy, it may cause birth defects or death to any unborn baby. Females are advised to avoid pregnancy while taking pomalidomide. The teratogenic potential of pomalidomide in humans cannot be ruled out. Females of childbearing potential must agree not to become pregnant while taking pomalidomide.
  - Using TWO reliable methods of birth control at the same time or complete abstinence from heterosexual intercourse [at least 28 days prior, while taking pomalidomide, during dose interruption, and 28 days after discontinuation of pomalidomide].
  - Continuation of TWO reliable methods of birth control or complete abstinence if therapy is interrupted.
  - That even if she has amenorrhea she must comply with advice on contraception.
  - Use of one highly effective method and one additional method of birth control AT THE SAME TIME. The following are examples of highly effective and additional effective methods of contraception:

- Highly effective methods:
  - Intrauterine device (IUD)
  - Hormonal (birth control pills, injections, implants)
  - Tubal ligation
  - Partner's vasectomy
- Additional effective methods:
  - Male condom
  - Diaphragm
  - Cervical cap
- Pregnancy tests before and during treatment, even if the patient agrees not to have reproductive heterosexual intercourse. Two pregnancy tests will be performed prior to receiving study drug, one within 10–14 days and the second within 24 hours of the start of pomalidomide.
- Frequency of pregnancy tests to be done:
  - Every week during the first 28 days of this study and a pregnancy test every 28 days during the patient's participation in this study if menstrual cycles are regular or every 14 days if cycles are irregular.
  - If the patient missed a period or has unusual menstrual bleeding.
  - When the patient is discontinued from the study and at Day 28 after study drug discontinuation if menstrual cycles are regular. If menstrual cycles are irregular, pregnancy tests will be done at discontinuation from the study and at Days 14 and 28 after study drug discontinuation.
- Stop taking pomalidomide immediately in the event of becoming pregnant and to call their study doctor as soon as possible.
- NEVER share pomalidomide with anyone else.
- Do not donate blood while taking pomalidomide and for 28 days after stopping pomalidomide.
- Do not breastfeed a baby while participating in this study and for at least 28 days after study drug discontinuation.
- Do not break, chew, or open pomalidomide capsules.
- Return unused pomalidomide to the investigator.

**3. Provide Pomalidomide Information Sheet to the patient.**

**Female not of childbearing potential (natural menopause for at least 24 consecutive months, a hysterectomy, or bilateral oophorectomy):**

**1. I counseled the female NOT of childbearing potential regarding the following:**

- Potential fetal harm (Refer to item #2 in FCBP).
- NEVER share pomalidomide with anyone else.
- Do not donate blood while taking pomalidomide and for 28 days after stopping pomalidomide.
- Do not break, chew, or open pomalidomide capsules.
- Return used pomalidomide capsules to the investigator.

**2. Provide Pomalidomide Information Sheet to the patient.**

**Male**

**1. I counseled the Male patient regarding the following:**

- Potential fetal harm (Refer to item #2 in FCBP).
- To engage in complete abstinence or use a condom when engaging in sexual intercourse (including those who have had a vasectomy) with a FCBP, while taking pomalidomide, during dose interruptions, and for 28 days after stopping pomalidomide.
- Males should notify their study doctor when their female partner becomes pregnant and female partners of males taking pomalidomide should be advised to call their healthcare provider immediately if they get pregnant.
- NEVER share pomalidomide with anyone else.
- Do not donate blood while taking pomalidomide and for 28 days after stopping pomalidomide.
- Do not donate semen or sperm while taking pomalidomide and for 90 days after stopping pomalidomide.
- Do not break, chew, or open pomalidomide capsules.
- Return unused pomalidomide capsules to the investigator.

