- Negative HBsAg and positive for hepatitis B core antibody: hepatitis B virus DNA by polymerase chain reaction (PCR) is necessary. Detectable hepatitis B virus DNA suggests occult hepatitis B
- Positive Hepatitis C virus antibody (HCVAb): hepatitis C virus RNA by PCR is necessary. Detectable hepatitis C virus RNA suggests chronic hepatitis C

217 History of clinically significant GI hemorrhage (Grade  $\geq$  2) in the 6 months prior to study day 1, unless agreed upon by the investigator and the Amgen Medical Monitor

218 Known positive results for Human Immunodeficiency Virus (HIV)

219 Unresolved toxicities from prior anti-tumor therapy, defined as not having resolved to Common Terminology Criteria for Adverse Events (CTCAE) version 4.03 Grade 1, or to levels dictated in the eligibility criteria with the exception of Grade 2 peripheral neuropathy, alopecia or toxicities from prior anti-tumor therapy that are considered irreversible (defined as having been present and stable for  $>$  4 weeks may be allowed if they are not otherwise described in the exclusion criteria AND there is agreement to allow by both the investigator and the Amgen Medical Monitor)

220 Anti-tumor therapy (chemotherapy, antibody therapy, molecular targeted therapy, or investigational agent) within 28 days or 5 half-lives whichever is shorter prior to study day 1.

221 Prior systemic radiation therapy must have been completed at least 28 days before study day 1. Prior focal radiotherapy completed at least 14 days before study day 1

222 Major surgery within 28 days prior to study day 1

223 Females of reproductive potential who are unwilling to use two methods of contraception, one highly effective and one additional effective contraception

method while on study through 30 days after receiving the last dose of study drug. Males unwilling to always use latex or synthetic condom during any sexual contact with females of reproductive potential while on study through 90 days after receiving the last dose of study drug. Acceptable highly effective methods of birth control are defined:

- Combined (estrogen and progestogen containing) hormonal contraception associated with inhibition of ovulation:
  - Oral
  - Intravaginal
  - Transdermal
- Progestogen-only hormonal contraception associated with inhibition of ovulation:
  - Oral
  - Injectable
  - Implantable
- Intrauterine device (IUD)
- Intrauterine hormone-releasing system (IUS)
- Bilateral tubal occlusion
- Vasectomized partner

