### Contraception

Females of reproductive potential must commit either to abstain continuously from heterosexual sexual intercourse or to use 2 methods of effective contraception simultaneously (1 highly effective form of contraception—tubal ligation, intrauterine device [IUD], hormonal [birth control pills, injections, hormonal patches, vaginal rings or implants] or partner's vasectomy and 1 additional effective contraceptive method—male latex or synthetic condom, diaphragm, or cervical cap). Contraception must begin 4 weeks prior to initiating treatment and continue during therapy, dose interruptions, and for 30 days after discontinuation of therapy. Reliable contraception is indicated even where there has been a history of infertility, unless this is due to hysterectomy. Females of reproductive potential should be referred to a qualified provider of contraceptive methods, if needed. Additional details are provided in Pomalidomide Risks of Fetal Exposure, Pregnancy Testing Guidelines and Acceptable Birth Control Methods ([Appendix H](#)), Pomalidomide Education and Counseling Guidance Document ([Appendix I](#)), and Pomalidomide Information Sheet for Subjects Enrolled in Clinical Research Studies ([Appendix J](#)).

Females of reproductive potential must have 2 negative pregnancy tests before initiating study treatment. The first test should be performed within 10 to 14 days of study treatment and the second test should be performed within 24 hours before study treatment. Once treatment has started and during dose interruptions, pregnancy testing for female subjects of reproductive potential should occur weekly during the first 4 weeks of treatment. Pregnancy testing should be repeated every 4 weeks thereafter for female subjects with regular menstrual cycles. For female subjects with irregular menstrual cycles,  $\pm$  7 days of a 28-day cycle, pregnancy testing should be performed every 2 weeks. Pregnancy testing and counseling should be performed if a subject misses her period or if there is any abnormality in her menstrual bleeding. Study treatment must be discontinued during this evaluation.

---

Postmenopausal females (> 45 years old and without menses for > 2 years) and surgically sterilized females are exempt.

Male subjects must use an effective barrier method of contraception during the study and for 90 days following the last dose if sexually active with a female of childbearing potential.

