Because pomalidomide is present in the semen of male subjects who receive it, they must always use a latex or synthetic condom during any sexual contact with females of reproductive potential and for up to 90 days after discontinuation of study treatment, even if they have undergone a successful vasectomy. Male subjects must agree not to donate sperm while being treated and for up to 90 days after discontinuing treatment.

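### The Appendix I male counselling checklist gives 28 days of condom use or abstinence after pomalidomide; the rest of the protocol requires 90

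*Protocol*

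**What the plan says.** The protocol states the male condom or abstinence period after treatment in five places.

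- **Appendix I, male checklist.** Men are to abstain or use a condom "with a FCBP, while taking pomalidomide, during dose interruptions, and for 28 days after stopping pomalidomide".
- **Section 7.2, exclusion criterion 223.** It excludes "Males unwilling to always use latex or synthetic condom during any sexual contact with females of reproductive potential while on study through 90 days", counted from the last dose of study drug.
- **Section 9.6, Contraception, general male rule.** "Male subjects must use an effective barrier method of contraception during the study and for 90 days following the last dose".
- **Section 9.6, Contraception, pomalidomide-specific rule.** The reason comes first: "Because pomalidomide is present in the semen of male subjects who receive it, they must always use a latex or synthetic condom". The scope and length of that obligation are then given as "any sexual contact with females of reproductive potential and for up to 90 days after discontinuation of study treatment".
- **Appendix H, Male Subjects, under the heading on what is required before starting study drug.** Abstinence or a condom is also required once treatment has ended, with the period given as "for at least 90 days following study drug discontinuation, even if he has undergone a successful vasectomy".

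The neighbouring rule on donating sperm or semen is 90 days wherever a period is given. Section 9.6 says "Male subjects must agree not to donate sperm while being treated and for up to 90 days after discontinuing treatment". Exclusion 223, the additional precautions in Appendix H, and the Appendix I male checklist itself also use 90 days.

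**The concern.** Appendix I is the form a counsellor works through with the patient, and Section 9.6 refers the reader to it. Its male section is worded as a record of what the man was told. If it carries a shorter period than the rule it implements, a site can complete it correctly and still give the wrong instruction.

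The subject is fetal exposure. Appendix H describes pomalidomide as teratogenic in rabbits and as an analogue of a known human teratogen. Appendix H also requires that counselling about "condom use during sexual contact with FCBP and the potential risks of fetal exposure must be conducted at a minimum of every 28 days", but that item does not say how long condom use must continue after treatment. The checklist is therefore the natural place for a counsellor to find the number.

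The point is also still live. Section 9.2.1.1 of the current protocol allows subjects with clinical benefit to switch formulation, so it anticipates people still on treatment. For any such man the post-treatment period lies ahead.

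**Working it through.** There is no sample size, power or error-rate figure to reproduce. The check sets the texts side by side and asks whether any reading reconciles them.

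| Place | Period after stopping | Counted from |
|---|---|---|
| Appendix I, male condom item | 28 days | stopping pomalidomide |
| Exclusion 223 | 90 days | last dose of study drug |
| Section 9.6, general male rule | 90 days | last dose |
| Section 9.6, pomalidomide rule | up to 90 days | discontinuation of study treatment |
| Appendix H, Male Subjects | at least 90 days | study drug discontinuation |
| Appendix I, semen donation item | 90 days | stopping pomalidomide |

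**Size.** With both periods starting on the same day, the form falls short by 90 − 28 = 62 days.

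**Could the 90 days belong to a different drug?** No. Section 9.6 gives pomalidomide in semen as the reason for the condom rule and attaches 90 days to it. Appendix H is the pomalidomide appendix. The semen-donation items in Appendices H and I attach 90 days to pomalidomide by name.

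**Could the different starting point explain it?** No. Section 9.2 defines study treatment as any combination of the three drugs. Sections 9.3.1.1 and 9.3.2.2 allow pomalidomide to stop while oprozomib and dexamethasone continue. Suppose treatment continues for *d* days after pomalidomide stops. The Section 9.6 period then ends *d* + 90 days after stopping pomalidomide, while the form's period ends at 28 days. The gap is (*d* + 90) − 28 = 62 + *d* days. On that definition it is never below 62.

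**Could *up to 90 days* in Section 9.6 permit 28?** Read alone it is a ceiling. However, the general male rule in the same section gives a flat 90 days, and Appendix H makes 90 a minimum. Those texts cannot be met with 28 days.

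**Could the shorter period be deliberate?** Nothing says so. The same checklist keeps 90 days for semen donation, and no reason is given for treating condom use differently. The women's post-treatment contraception period in Appendices H and I is 28 days, so a carry-over into the male item is plausible. The documents do not confirm that.

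**The case against.** The case on the other side does not reconcile the figures, but several of its points deserve an answer.

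- **Appendix H itself places men under a 28-day heading.** The male counselling-frequency item sits in a block headed as covering study participation and the 28 days after study drug stops. This is true, and that heading may be left as it is. It governs how long counselling continues. It does not replace the 90-day condom rule stated earlier in the same appendix.
- **Some male 90-day periods are tied to oprozomib.** In exclusion 223 the sperm-donation restriction is counted from the last oprozomib dose, and Section 12.3 does the same for partner pregnancy reporting. The condom wording in exclusion 223 and the general rule in Section 9.6 name no drug. This stands, so the argument should rest mainly on the Section 9.6 sentence about semen, which does name pomalidomide.
- **Changing only the number leaves the starting point unsettled.** A man who stops pomalidomide and continues oprozomib would, on the corrected form, still finish *d* days before the Section 9.6 period ends. This stands as a residual difference. It is smaller in kind, because the stated reason for the condom rule is pomalidomide.
- **Practical harm is not shown.** Sites are bound by the longer text, exclusion 223 screens out unwilling men, and the semen-donation item on the same page prints 90 days. The Appendix J sheet given to patients is not available in the reviewed documents, so what men receive in writing is unknown. This limits the weight of the point. It does not make the form correct.

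**Conclusion.** The concern holds. The condom and abstinence item for men in Appendix I contradicts exclusion 223, Section 9.6 and Appendix H, and no reading of the documents reconciles 28 days with 90. The shortfall is 62 days when the periods start together. It is longer if pomalidomide stops before the rest of study treatment, taking study treatment as Section 9.2 defines it.

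The error affects only men who receive pomalidomide and have sexual contact with a female of childbearing potential. The documents do not give their number. It is a mistake on a safety form that should be corrected. It is not evidence that anyone was left unprotected, and it does not touch the endpoints, the dose-escalation decisions or the analysis.

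**What to change.** In the Appendix I male checklist, change the post-treatment period for abstinence or condom use from 28 days to at least 90 days after stopping pomalidomide. This keeps the existing starting point, which the semen-donation items in Appendices H and I share. If the sponsor prefers to count from the last dose of study treatment, in line with Section 9.6, both semen-donation items should move with it.

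Check that the Appendix J information sheet gives the same period, then reissue the counselling form to sites.

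Optionally, in Section 9.6 replace *up to* with *at least* in both 90-day statements (condom use and sperm donation), so that they match Appendix H.

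The cost is one figure in the next amendment and a reissued form. Sample size, dosing and analysis do not change.
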